
#### **4.5.2. Immunogenicity Variables**

Individual HAI and Neut results will be reported by the central immunology laboratory for the homologous vaccine strain, A/Hong Kong/125/2017 (H7N9) and heterologous H7N9 strains, A/Shanghai/2/2013 and A/Guangdong/17SF003/2016. Assay results are reported as a reciprocal titer with values of  $10 \times 2^k$ , where  $k=0, 1, 2$ , etc. The lower limit of detection for the HAI and Neut assays is 10, values below the lower limit of detection are imputed for analysis as one-half the limit of detection ( $10/2 = 5$ ). For analysis, the geometric mean (calculated on natural log scale) of repeated results for each sample will be computed and used as the response for all subsequent calculations. The variation arising from multiple measurements for an individual at a single time point is not used in subsequent calculations. See Section 3.3 for definitions of derived variables for the analysis of HAI and Neut data.

An addendum to the SAP will be generated to outline the planned analyses for NA antigen specific antibody responses and HA stem-specific antibody responses when assay development is complete, and results are available.

All immunogenicity data will be uploaded into the SDCC's electronic data capture system.

---

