In general, clinical studies evaluating vaccines made from novel avian influenza viruses (e.g., A/H5N1, A/H7N7, 2013 A/H7N9) suggest that these vaccines are substantially less immunogenic than those from other novel subtypes (e.g., 2009 A/H1N1 pandemic virus), even when administered at high HA dosages [27, 28]. Due to the poor immunogenicity of A/H5 and A/H7 vaccines, the inclusion of adjuvants was evaluated to assess their ability to boost anti-viral serum IgG levels. In the US, aluminum salts are licensed as adjuvants in combination with several vaccines; however, their use in subvirion influenza A/H5N1 vaccines has shown either no effect or a very modest enhancement of immune responses compared to non-aluminum salt containing formulations [29-31]. In contrast, the use of oil-in-water emulsion adjuvants, most notably proprietary adjuvants AS03 and MF59 produced by GSK and Novartis (now Seqirus), respectively, has resulted in increased antibody responses to IIVs containing novel HAs in numerous clinical trials [32-36]. In an early study, dosage levels ranging from 3.75 to 30 mcg of A/H5N1 antigen administered with or without AS03 resulted in significant increases in antibody geometric mean titers (GMTs) in subjects who received the adjuvanted formulations [34]. These GMTs met the Committee for Medicinal Products for Human Use (CHMP) criterion for seroconversion rate (>40%) after a single dose with adjuvant. Following the second vaccine dose, all adjuvanted formulations complied with both CHMP and US Food and Drug Administration (FDA) criteria for seroconversion and seroprotection rates, whereas from the non-adjuvanted treatment arms only the 30 mcg formulation met the CHMP criterion for seroconversion [34]. GSK received approval for the registration of a pre-pandemic AS03-adjuvanted, monovalent inactivated influenza A/H5N1 virus vaccine by European regulatory authorities in 2008 and FDA approval of their Biologics License Applications (BLA) for an Influenza A (H5N1) Virus Monovalent Vaccine Adjuvanted (with AS03) in 2013.

Following the 2009 emergence of the novel A/H1N1 pandemic virus, the European Commission granted marketing authorization of GSK's egg-derived AS03-adjuvanted monovalent inactivated

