2.2 Scientific Rationale

As part of the US Government's past pandemic preparedness efforts, Sanofi Pasteur under contract to the Biomedical Advanced Research and Development Authority (BARDA)/DHHS, produced several novel pre-pandemic vaccines that were or are currently being evaluated by NIAID's VTEU sites to assess their safety, reactogenicity and immunogenicity when mixed prior to administration with either AS03 or MF59 oil-in-water adjuvants manufactured by GSK and Seqirus, respectively. In general, these "mix and match" clinical trials have demonstrated that adjuvant use results in a significant dose-sparing effect.

The large number of human infections starting with the "fifth wave" of outbreaks in late 2016 has increased the pandemic risk potential of influenza A/H7N9 viruses circulating in China. The Yangtze River Delta lineage, a distinct A/H7N9 viral lineage, has now emerged and has been associated with many of the fifth wave cases. Fifth wave A/H7N9 viruses have led to a broader geographic spread of infected birds and human cases within China than previously reported. Further, several influenza A/H7N9 viruses in the Yangtze River Delta lineage have recently acquired genetic changes characteristic of highly pathogenic avian influenza (HPAI) viruses and have now shown an increased ability to infect and kill poultry [56, 59]. To date, no cases of A/H7N9 from the new viral lineage have been identified in birds or people infected outside of China; however, a few cases have been identified in Hong Kong and Taiwan in infected travelers returning from China. Importantly, antigenic analysis of the fifth wave influenza A/H7N9 viruses and serological studies indicate that the stockpiled 2013 A/H7N9 IIV manufactured several years

ago does not induce protective HAI or Neut antibodies against the Yangtze River Delta lineage. Hence, there is broad consensus across DHHS and interagency leadership that a new vaccine should be developed that would be effective against the currently predominating influenza A/H7N9 viruses.

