#### Immunogenicity:

- For HAI and Neut antibodies, percentage of subjects achieving seroconversion against the 2017 influenza A/H7N9 study vaccine virus (defined as either a pre-vaccination titer <10 and a post-vaccination titer  $\geq 40$  or a pre-vaccination titer  $\geq 10$  and a minimum four-fold rise in post-vaccination antibody titer) approximately 21 days after study vaccination.
- For HAI and Neut antibodies, percentage of subjects achieving titer  $\geq 40$  against the 2017 influenza A/H7N9 study vaccine virus approximately 21 days after study vaccination.
- Geometric mean titers (GMTs) of serum HAI and Neut antibodies against the 2017 influenza A/H7N9 study vaccine virus approximately 21 days after study vaccination.

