## 8. IMMUNOGENICITY EVALUATION

Analysis of all immune responses will be conducted using the PP population. In addition, primary endpoint analyses will be conducted with the mITT population. Immune responses in terms of strain-specific A/H7N9 HAI and Neut antibody titers will be summarized by study group at each time point. Descriptive summary statistics will be provided for all assays and time points including number of subjects with non-missing results, percentage of subjects with titers  $\geq 40$ , percentage of subjects achieving seroconversion, and GMTs along with corresponding 95% CIs. Exact CIs will be presented for proportional endpoints. Summaries of primary and secondary immunogenicity endpoints are presented in [Table 22](#), [Table 23](#), [Table 24](#), and [Table 25](#).

Reverse cumulative distribution (RCD) curves will be presented for HAI and Neut antibody titers against A/Hong Kong/125/2017 (H7N9), A/Shanghai/2/2013 (H7N9), and A/Guangdong/17SF003/2016 (H7N9) strains. Plots for each assay will be generated with 4 panels (pre-vaccination, 7 days post vaccination, 21 days post vaccination, and 180 days post vaccination) and separate curves within each panel for each study group and stratum, as shown in [Figure 2](#), [Figure 3](#), [Figure 4](#), [Figure 5](#), [Figure 6](#), [Figure 7](#), [Figure 8](#), and [Figure 9](#).

HAI and Neut antibody GMTs against A/Hong Kong/125/2017 (H7N9), A/Shanghai/2/2013 (H7N9), and A/Guangdong/17SF003/2016 (H7N9) will be presented graphically with corresponding 95% CIs in [Figure 10](#), [Figure 11](#), [Figure 12](#), [Figure 13](#), [Figure 14](#), [Figure 15](#), [Figure 16](#), and [Figure 17](#).

The spearman correlation between HAI and Neut antibody titers will be calculated at each time point over all stratum and group combinations for each strain. The correlation will be depicted in scatterplots as depicted in [Figure 18](#), [Figure 19](#), [Figure 20](#), and [Figure 21](#).

Individual HAI and Neut assay results will be provided in [Listing 9](#) and [Listing 10](#), respectively.

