Time Point	2013 A/H7N9 IIV + MF59 (N=X)		2013 A/H7N9 IIV + AS03 (N=X)		2013 A/H7N9 IIV 15 mcg or 45 mcg unadjuvanted (N=X)		2013 A/H7N9 IIV with MF59/AS03 then 2013 A/H7N9 IIV 15 mcg (N=X)		A/H7 IIV Naïve (N=X)	
	3.75 mcg A/H7N9 (N*=X)	3.75 mcg A/H7N9 + AS03 (N*=X)	3.75 mcg A/H7N9 (N*=X)	3.75 mcg A/H7N9 + AS03 (N*=X)	3.75 mcg A/H7N9 (N*=X)	3.75 mcg A/H7N9 + AS03 (N*=X)	3.75 mcg A/H7N9 (N*=X)	3.75 mcg A/H7N9 + AS03 (N*=X)	3.75 mcg A/H7N9 (N*=X)	3.75 mcg A/H7N9 + AS03 (N*=X)
GMFR (95% CI) a	xxx.x (xxx.x,xxx.x)	xxx.x (xxx.x,xxx.x)	xxx.x (xxx.x,xxx.x)	xxx.x (xxx.x,xxx.x)	xxx.x (xxx.x,xxx.x)	xxx.x (xxx.x,xxx.x)	xxx.x (xxx.x,xxx.x)	xxx.x (xxx.x,xxx.x)	xxx.x (xxx.x,xxx.x)	xxx.x (xxx.x,xxx.x)
Seroconversion - % (95% CI) b	xx (xx, xx)	xx (xx, xx)	xx (xx, xx)	xx (xx, xx)	xx (xx, xx)	xx (xx, xx)	xx (xx, xx)	xx (xx, xx)	xx (xx, xx)	xx (xx, xx)
180 Days Post Vaccination										
n	x	x	x	x	x	x	x	x	x	x
GMT (95% CI) a	xxx.x (xxx.x,xxx.x)	xxx.x (xxx.x,xxx.x)	xxx.x (xxx.x,xxx.x)	xxx.x (xxx.x,xxx.x)	xxx.x (xxx.x,xxx.x)	xxx.x (xxx.x,xxx.x)	xxx.x (xxx.x,xxx.x)	xxx.x (xxx.x,xxx.x)	xxx.x (xxx.x,xxx.x)	xxx.x (xxx.x,xxx.x)
Titer ≥ 1:40 - % (95% CI) b	xx (xx, xx)	xx (xx, xx)	xx (xx, xx)	xx (xx, xx)	xx (xx, xx)	xx (xx, xx)	xx (xx, xx)	xx (xx, xx)	xx (xx, xx)	xx (xx, xx)
GMFR (95% CI) a	xxx.x (xxx.x,xxx.x)	xxx.x (xxx.x,xxx.x)	xxx.x (xxx.x,xxx.x)	xxx.x (xxx.x,xxx.x)	xxx.x (xxx.x,xxx.x)	xxx.x (xxx.x,xxx.x)	xxx.x (xxx.x,xxx.x)	xxx.x (xxx.x,xxx.x)	xxx.x (xxx.x,xxx.x)	xxx.x (xxx.x,xxx.x)
Seroconversion - % (95% CI) b	xx (xx, xx)	xx (xx, xx)	xx (xx, xx)	xx (xx, xx)	xx (xx, xx)	xx (xx, xx)	xx (xx, xx)	xx (xx, xx)	xx (xx, xx)	xx (xx, xx)

Note: N = Number of subjects in the modified intent-to-treat population in the given stratum; N\* = Number of subjects in the modified intent-to-treat population in the given stratum and study group; n = number of subjects with available results; GMT = Geometric Mean Titer; GMFR = Geometric Mean Fold Rise.

a Confidence Interval calculated based on the student's T distribution.

b Exact binomial confidence interval calculated using the Clopper-Pearson methodology.

Tables with similar format:

**Table 23: Summaries of Hemagglutination Inhibition Antibody Against A/Hong Kong/125/2017 (H7N9) by Study Day, Stratum and Study Group, Per Protocol Population\***

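### When about 90% or more of a group's titers are below 10, the SAP's Student-t interval on the GMT under-covers, and it prints as 5.0 (5.0, 5.0) when all are below 10; the SAP has no rule for such cells

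*SAP*

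**What the plan says.** The SAP lists among its primary endpoints "Geometric mean titers (GMTs) of serum HAI and Neut antibodies against the 2017 influenza A/H7N9 study vaccine virus approximately 21 days after study vaccination". On the assay, SAP 4.5.2 states "The lower limit of detection for the HAI and Neut assays is 10" and that "values below the lower limit of detection are imputed for analysis as one-half the limit of detection". The analysed titer is the geometric mean of two replicates (SAP 3.3 and 4.5.2).

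SAP 8 promises "GMTs along with corresponding 95% CIs" by group and time point. Footnote a of Table 22 gives the method for GMT and GMFR: "Confidence Interval calculated based on the student's T distribution". Tables 23-25 share that format, and the same footnote recurs through the covariate and heterologous-strain tables. Percentage with titer at or above 40 and percentage seroconverting get exact Clopper-Pearson intervals in the same tables. Reverse cumulative distribution curves are planned by group and visit.

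The SAP has no rule for a cell in which most or all titers are below 10, no row for the share detectable, and no sensitivity analysis of the substitution. The normality condition in SAP 8.3.2 applies to the linear regression of log titer, not to these intervals.

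**The concern.** A t interval measures the spread of the analysed values. When most of those values are one substituted constant, the spread mainly reflects the substitution. In the extreme case it is zero, and a cell in which nothing could be measured carries the narrowest interval in the table.

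This matters because Protocol 11.2 describes the trial as an estimation exercise and Tables 22-25 are topline tables. Some cells could plausibly be affected. Protocol 2.1 says of avian-virus vaccines that "these vaccines are substantially less immunogenic than those from other novel subtypes". It describes an H5N1 study in which, after two doses, only the 30 mcg unadjuvanted arm met the European seroconversion criterion. Group 10 receives a single unadjuvanted 3.75 mcg dose with no prior H7 vaccine. Exclusion criteria 24-26 remove people with known H7 infection or substantial poultry contact, so the Day 1 rows of both naive groups may also sit near the floor.

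**Working it through.** **Inputs.** Floor value 5, detection limit 10 and titers on the scale 10 × 2^k (SAP 4.5.2); group sizes 30 and 50 (SAP Table 1); 95% t interval (Table 22 footnote a), taken to be on the log scale, which the footnote does not state. The share detectable, p, is not in the documents and is assumed over a range.

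**The plan's own precision figure.** The SAP gives none for a GMT. Its worst-case exact binomial interval at 50% response and N=30 (Table 6, 31-69) reproduces as 31.3-68.7.

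**Degenerate cell.** With all 30 values at 5, the SD is 0 and the interval is 5.0 (5.0, 5.0). If Day 1 values are also all 5, GMFR is 1.0 (1.0, 1.0).

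**One detectable titer of 10 among 30.** In log2 units above 5, the mean is 1/30 = 0.0333, the SD is √(1/30) = 0.183 and the SE is 0.0333. With t(29) = 2.045 the half-width is 0.068. Back-transformed: 5.12 (4.88, 5.36). The lower limit lies below 5, the smallest value the data can take.

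**Coverage.** Assume that a share p has titers 10/20/40/80 with weights 0.50/0.25/0.15/0.10 and the rest are set to 5. The mean log2 step above 5 among detectable subjects is 0.50 + 0.50 + 0.45 + 0.40 = 1.85, so the true floored GMT is 5 × 2^(1.85p). Coverage of that value comes from 20,000 simulated samples per setting, one reading per sample.

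| Detectable p | True floored GMT | P(none detectable), n=30 = (1−p)^30 | Coverage, n=30 | Coverage, n=50 |
|---|---|---|---|---|
| 1% | 5.06 | 74% | 26% | 39% |
| 2% | 5.13 | 54% | 46% | 64% |
| 5% | 5.33 | 21% | 79% | 82% |
| 10% | 5.68 | 4% | 82% | 87% |
| 20% | 6.46 | 0.1% | 90% | 92% |
| 30% | 7.35 | <0.1% | 92% | 93% |

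Up to 5% detectable, n=30 coverage is close to 1 − P(none detectable), so zero-width intervals explain nearly all the loss. At 10% the loss comes mainly from samples with only a few detectable titers. There, 17.4% of intervals lie wholly below the true value and 0.2% wholly above.

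A second model, log2-normal titers with assumed SD 1.0 to 2.0, gives n=30 coverage of 91-92% at 80% below 10, 83-87% at 90%, 78-79% at 95% and 46% at 98%.

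**What 0/30 supports.** The exact upper limit on the share detectable is 1 − 0.025^(1/30) = 11.6%. The floored GMT could then be up to 5 × 2^0.1157 = 5.4 if detectable titers are 10, or 5 × 2^(3 × 0.1157) = 6.4 if they are 40. For 0/50 the limit is 7.1%, giving 5.3 to 5.8.

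**The case against.** **No stated expectation of undetectable titers.** A reader might infer that the protocol expects these groups to be undetectable. It does not say so. Protocol 2.1 is comparative. Protocol 2.2 says the 2013 vaccine "does not induce protective HAI or Neut antibodies against the Yangtze River Delta lineage", and not protective is not the same as below 10. That sentence concerns primed subjects before boosting and says nothing of Group 10 at Day 21. The planning tables consider responder rates of 10% to 90%. Under the weights above, 10% at or above 40 needs p = 0.10/0.25 = 40%, where coverage is 93% (n=30) and 94% (n=50). This stands, with one limit: the 10-90% range is a generic power grid and not a forecast for Group 10.

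**Small on the titer scale.** An upper limit of 5.4 to 6.4 in place of 5.0 is 0.12 to 0.35 of a two-fold dilution, still below the detection limit. This stands.

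**Information already shown.** With 0/30 at or above 40, the same table prints 0 (0, 12). The curves show the whole distribution, and Listings 9 and 10 give each replicate. This stands in part: the exact row cannot separate a group wholly below 10 from one wholly at 20, and the curves carry no interval.

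**Duplicates.** Replicates of below 10 and 10 give √(5 × 10) = 7.07, which is off the floor but not at or above 10. With assumed replicate SD 0.5 and between-subject SD 1.5 (log2), the chance of a zero-width interval at n=30 falls from 21% to 12% at 95% of readings below 10, and from 4% to 1% at 90%. This stands and shapes the wording of the fix.

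**Between-group effects.** Adjuvant and priming effects are estimated in the SAP 8.3.2 regressions, which this point does not address. The summary shells contain no GMT ratio.

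**Conclusion.** The gap is real and conditional. From about 90% of titers below 10, the t interval on the floored GMT under-covers, almost always by sitting too low, and with none detectable it has no width. With about 20% or more detectable, coverage is roughly 90-95% and the method is serviceable.

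Two stronger readings are tempting. One is that the primary GMT intervals are far too narrow in general; the coverage results contradict that outside heavily censored cells. The other is that certain groups will be at the floor; no document gives an expected GMT or share below 10, so for Group 10 and the naive Day 1 rows this remains a plausible inference.

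All coverage figures rest on assumed detectable shares and titer distributions, single readings, and a log-scale interval. The zero-width result when every analysed titer is 5 needs no distributional assumption. The case for acting is that the error bar would be wrong in an identifiable type of cell of a primary-endpoint table and is cheap to correct. No conclusion of the trial is shown to depend on it.

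**What to change.** In Tables 22-35 and 44-47:

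1. Add a row at each time point: percentage with a detectable titer (at least one replicate at or above 10, so analysed titer above 5), with exact Clopper-Pearson 95% interval. Defining it by replicate avoids misclassifying a 7.07.
2. Add a footnote: where no titer in a cell is detectable, show the GMT as <10 (analysis value 5) without a t-based interval, treat GMFR likewise where its SD is zero, and report the exact interval for the percentage detectable. Where fewer than about 10% are detectable, keep the t interval but flag it as unreliable. State this exception in SAP 8, which otherwise promises an interval for every GMT.

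The 10% flag is a judgement based on the coverage table. A broader rule that suppresses intervals, for example below 20% detectable, would remove intervals with about 90% coverage.

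A censored-likelihood GMT is optional, only for cells with enough detectable titers, and should be labelled as a different estimand. At n=30, assumed SD 1.5 and 90% below 10, its median interval was 0.1-6.1 against 5.0-6.4 for the t interval, and only 55% of simulated trials had the two distinct detectable values needed to fit it.

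Cost: SAP wording, one row and one footnote, no new data. A few cells would show no GMT interval.

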## 5. SAMPLE SIZE CONSIDERATIONS

This study is planned to enroll up to 420 subjects. The majority of subjects will be recruited from the population of subjects who received the 2013 A/H7N9 IIV in DMID Protocols 13-0032 and 13-0033. The sample size for this study was selected using estimates of recruitment based on the number of subjects completing these historical protocols and by 2013 A/H7N9 IIV vaccination history. [Table 4](#) summarizes the vaccination history in these protocols and potential enrollment into this study. While this study is not designed to test any specific null hypothesis, the following tables illustrate the precision and power that is available for select estimates and comparisons of interest.

[Table 5](#) indicates the probability of observing one or more safety events, such as solicited injection site or systemic reactogenicity events or an unsolicited non-serious AE of a particular type for treatment arms (N=30, 50), in all subjects receiving adjuvant (N=210) or in the trial as a whole (N=420).

Binomial confidence intervals (CIs) are widest (have the least precision) when the response rate is 50%. [Table 6](#) is presented to indicate the worst-case scenario for precision of observed exact (Clopper-Pearson) binomial confidence intervals.

[Table 7](#) illustrates the minimum detectable differences in the proportion of subjects responding (e.g. attaining seroconversion or a titer  $\geq 40$ ) between any two treatment arms (N=30 or 50) using a two-sided Likelihood Ratio Test with  $\alpha = 0.05$ . From previous experience with single dose studies, it is assumed that up to 3% of subjects will be excluded from the per protocol analysis with minimal effect on these calculations. Seroconversion rates of 10% to 90% are considered.

## 6. GENERAL STATISTICAL CONSIDERATIONS

### 6.1. General Principles

All continuous variables will be summarized using the following descriptive statistics: n (non-missing sample size), mean, standard deviation, median, maximum and minimum. The frequency and percentages (based on the non-missing sample size) of observed levels will be reported for all categorical measures. In general, all data will be listed, sorted by study group and subject, and when appropriate by visit number within subject. All summary tables will be structured with a column for each Study Group in the following order:

- Group 1: 1 or 2 doses 2013 A/H7N9 + MF59 | 2017 A/H7N9 IIV 3.75mcg + AS03
- Group 2: 1 or 2 doses 2013 A/H7N9 + MF59 | 2017 A/H7N9 IIV 3.75mcg
- Group 3: 1 or 2 doses 2013 A/H7N9 + AS03 | 2017 A/H7N9 IIV 3.75mcg + AS03
- Group 4: 1 or 2 doses 2013 A/H7N9 + AS03 | 2017 A/H7N9 IIV 3.75mcg
- Group 5: 1 or 2 doses 2013 A/H7N9 15mcg or 45mcg | 2017 A/H7N9 IIV 3.75mcg + AS03
- Group 6: 1 or 2 doses 2013 A/H7N9 15mcg or 45mcg | 2017 A/H7N9 IIV 3.75mcg
- Group 7: 2013 A/H7N9 + MF59 or AS03 then 2013 A/H7N9 15mcg | 2017 A/H7N9 3.75mcg + AS03
- Group 8: 2013 A/H7N9 + MF59 or AS03 then 2013 A/H7N9 15mcg | 2017 A/H7N9 3.75mcg
- Group 9: A/H7N9 IIV-Naïve | 2017 A/H7N9 3.75mcg + AS03
- Group 10: A/H7N9 IIV-Naïve | 2017 A/H7N9 3.75mcg

All tables will be annotated with the total population size relevant to that table/arm, including any missing observations.

### 6.2. Timing of Analyses

#### 6.2.1. CSR

Once the last subject completes the visit that occurs approximately at Day 366, the clinical database will be cleaned, monitored, and locked. The CSR will be completed when all safety data through Day 366 and all humoral immunogenicity data through Day 180 are completed and uploaded.

Upon receipt of humoral immunogenicity against influenza A/Hong Kong/125/2017 (H7N9), A/Shanghai/2/2013 (H7N9), and A/Guangdong/17SF003/2016 (H7N9) strains through Day 180 and subsequent non-clinical data lock, a subset of predefined “topline tables” will be generated by the SDCC concurrently with CSR generation. These tables will include summaries of safety and immunogenicity data and will represent the final analyses of primary and secondary endpoints; as such no p-value adjustment is required. These analyses may be made available to the sponsor for planning subsequent trials and to the lead PI for publication. Tables to be included in the topline set are indicated in this document with the symbol \* in the title.

Analysis of exploratory immunogenicity endpoints may be performed and released as the data are available from the research laboratory. Any such analyses would be considered the final analysis for the endpoint and included in the CSR. Additional exploratory immunogenicity endpoint data not available at the time of CSR preparation may be included in an addendum to the CSR

---

